7.10 Cost coverage analysis

A cost coverage analysis has been conducted by the team: all tests listed in the Schedule of Events will be considered 'research' and paid for with the study funds. Any additional tests (not listed above) that is necessary for patient care will be considered standard of care and will be billed to the patient or the insurer.

8) ASSESSMENT OF SAFETY

8.1 Specification of Safety Parameters

Safety parameters will include data deriving from history and physical examination performed at each visit, laboratory data and results of functional and imaging tests. To enhance detection of adverse events between visits, all patients will be encouraged to

contact the research team at any time with concerns or any perceived changes in their healthcare status.

Disease-related data (HF-related) will be assessed including changes in symptoms (or new symptoms), functional capacity, vital signs (including weight), renal function, or any significant changes in medications.

Data specific to the treatment will also be assessed. The patient will be asked about symptoms and examined for signs of infection. Considering that Anakinra may mask signs of infection such as fever, a low threshold for further investigation will be advocated. A complete cell count will be measured at each visit to exclude the unusual cases of Anakinra-related neutropenia (ANC<1000), for which suspension of active treatment will be considered until return to a value of ANC>1,800/mm³ (or >1,000/mm³ if patient is African-American). Cessation of Anakinra will not be mandatory. Changes to treatment for side-effects or unanticipated problems will be performed without breaking the randomization code, unless deemed necessary for the treatment of the individual patient by the physician, in which case the physician will be made aware while the remainder of the team, especially the investigators performing and interpreting the tests, will be maintained blinded. The risks of the tests performed have been described above. In order to reduce risk, the procedures will be performed by skilled practitioners in the standard clinical fashion. Abnormal or incidental findings will be handled on a case by case basis as clinically indicated.

8.2 Data collection

The principal investigator at the site will be provided with a data collection sheets or case report forms on which data about the individual subject will be collected. The subjects will be identified as a consecutive number (i.e., 01, 02, ...08). The data collected on these forms will not contain any personal identifiable information. A database of de-identified data will be created.

Anakinra is given as a subcutaneous injection of 100 mg (0.67 mL) daily or every other day in patients with severe impairment in renal function. There is no loading dose and no dose-adjustments needed with age, weight, or liver failure. Drug-to-drug interactions have not been reported. There are no known toxic effects of anakinra in pregnancy (category B), however pregnant women will be excluded from this research study.

In a study following patients with rheumatoid arthritis for up to 3 years, anakinra was generally well-tolerated with few side effects.

The most likely side effects associated with the use of anakinra include:

- Injection site reaction (>10%, up to 50%, but infrequently leading to interruption of treatment <5%)
- Serious Infection (1.8% in anakinra vs 0.6% in placebo in clinical trial of rheumatoid arthritis);
- Headache, generally mild and self-limiting (1-10%);
- Diarrhea, generally mild and self-limiting (1-10%);
- Nausea, generally mild and self-limiting (1-10%)
- Neutropenia (rare, <1%, reversible).
- Hypersensitivity reaction (rash, anaphylaxis, arthritis)(rare, 1-2%).

The injection site reactions are by far the most common adverse reaction. The reactions present as painful irritation/redness at the site of injection usually occurring 1-2 weeks after start of treatment. They are responsive to topical steroids and/or antihistamine therapy. The reactions are common (up to 50%) but are rarely cause of discontinuation of therapy (<5%).

Despite the increase in risk of serious infection with anakinra, such events are rather rare (<2% during chronic treatment). Anakinra is indeed not associated with an increase in infection-related mortality, nor associated with opportunistic infection. Anakinra may, however, mask some of the signs of infection such as fever and leukocytosis, and therefore education on the need to be aware of risk of infection is warranted. Nevertheless when given to patients with sepsis in the setting of a clinical trial anakinra had no negative effect on survival. While anakinra is postulated to prevent inflammatory-based hypercoagulability, anakinra has not been associated with any appreciable bleeding risk in pre-clinical, clinical, or post-marketing surveillance (including animal studies at >100X the clinically relevant dose).

There is a social/psychological risk in this study of breaching confidentiality and having a patient's diagnosis discovered. The likelihood of this occurring, however, is very low, and not different from the patient receiving clinical care at the same time. The number of study visits could impact some aspects of the patients' social lives. Loss of confidentiality is a potential risk. However, except when required by law patients will not be identified by name, social security number, address, telephone number or any other personal identifier. Study related tests may be reported to the NHLBI but patients will not be identified.

The following risks pertain to the different tests that are being used for monitoring the treatment responses:

- ECG: no greater than minimal risk.
- Blood draw: minor bleeding (rare) and infection (extremely rare) at puncture site
- Cardio pulmonary exercise test (CPX): very low risk of rhythm disturbance of the heart and syncope. With adequate medical supervision extremely low risk of serious complication. A physician will be present during the CPX.
- Bioimpedance analysis: no greater than minimal risk
- Echocardiogram: no greater than minimal risk.
- Questionnaires: the PHQ-9 is a depression screening tool that includes questions that may be upsetting to some patients

All AEs must be graded for severity and relationship to study product.

Severity of Event: All AEs will be assessed by the study investigator using the following guidelines:

- Mild: events that require minimal or no treatment and do not interfere with the patient's daily activities.
- Moderate: events that result in a low level of inconvenience or concern with the therapeutic measures. Moderate events may cause some interference with functioning and may require systemic drug therapy or other treatment.
- Severe: events interrupt a patient's usual daily activity and may require systemic drug therapy or other treatment. Severe events are usually incapacitating.
- Life threatening: any adverse drug experience that places the patient or subject, in the view of the investigator, at immediate risk of death from the reaction as it occurred

(i.e. does not include a reaction that might have caused death had it occurred in a more severe form).

A dedicated AE form will be used to capture of pertinent information about the event. Changes in the severity of an AE will be documented to allow an assessment of the duration of the event at each level of intensity to be performed. Adverse events characterized as intermittent require documentation of onset and duration of each episode.

Relationship to the intervention: All suspected AEs must have their relationship to study intervention assessed using the terms: associated or not associated. In a clinical trial, the study intervention must always be a suspect. To help assess, the following guidelines are used to assess causality:

- **Definitely related:** The event is temporally related to the administration of the study intervention and, in the opinion of the investigator, no other etiology explains the event.
- **Probably related:** The event is temporally related to the administration of the study intervention and represents, in the opinion of the investigator, the most plausible explanation of the event.
- **Possibly related:** The event is temporally related to the administration of the study intervention but, in the opinion of the investigator, it does not represent the most likely explanation of the event.
- **Definitely Unrelated:** The event is temporally independent of study intervention and/or the event appears, in the opinion of the investigator, to be explained by another etiology.

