Appendix: DSMB Charter**1) KEY PERSONNEL**

Please refer to the IRB Roster and Delegation Log for a complete personnel list

Name	Role	Institution/ Division
[name]/PhD	Medical Responsible PI	VCU, Cardiology
[name] [name]	Study Operation PI	VCU, School of Pharmacy
[name]	Clinical Trial Operations	VCU, Cardiology
[name]	CPX Core Lab	University of Illinois, Chicago
[name]	Investigational Pharmacy	VCU, School of Pharmacy
[name]	Biostatistician	VCU, Biostatistics
[name]	DSMB Chair	University of Florida, Cardiology
[name]	DMSB member	VCU, Infectious disease
[name]	DSMB member	Virginia Cardiovascular Specialists
[name]	DSMB member	VCU, Immunology
[name]	DSMB member	VCU, Biostatistics, CCTR
[name]	DSMB liaison	VCU, Pauley Heart Center

Abbreviations: DSMB=Data Safety Monitoring Board

2) PROTOCOL SUMMARY

Title: Interleukin-1 Blockade in Recently Decompensated Heart Failure

Population: 102 patients (age >21 years) with a clinical diagnosis of systolic heart failure, and recent (within 2 weeks of discharge) hospitalization for heart failure

Site(s): Virginia Commonwealth University, Richmond, VA

Study Duration: 40 months

Description: Phase II clinical trial of Anakinra (or Placebo) (2:1 allocation) for the treatment of patients with recently decompensated systolic (LVEF≤40%) heart failure and increased systemic inflammation (CRP>2 mg/L)

Objectives: To determine the effects of Anakinra (or Placebo) on peak of aerobic exercise capacity (peak VO₂) measured with a cardiopulmonary test after 24 weeks

[figure not shown]
Study Design: Single-center, randomized, double-blinded, placebo-controlled clinical trial with allocation to Anakinra 100 mg daily or placebo in 2:1 ratio for 24 weeks

Estimated Time to Complete Enrollment: 36 months

Estimated Time to:

- First patient in:** 6-12 months from funding
- Last patient in:** 34 months from first patient enrolled
- Last patient out:** 40 months from first patient enrolled

3) SCHEMATIC OF STUDY DESIGN

4) DESCRIPTION

The **REDHART2** (*RE*cently *D*ecompensated *H*eart failure *A*nakinra *R*esponse *T*rial 2) study is a phase II clinical trial of anakinra or placebo to improve aerobic exercise capacity in patients with recently decompensated systolic heart failure (HF).

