6.3 Exclusion Criteria

Subjects will not be eligible if they meet any one of the following 15 exclusion criteria.

1. The primary diagnosis for admission is NOT decompensated heart failure, including

- diagnosis of acute coronary syndromes, hypertensive urgency/emergency, tachy- or brady-arrhythmias.
- 2. Concomitant clinically significant comorbidities that would interfere with the execution or interpretation of the study including but not limited to acute coronary syndromes, uncontrolled hypertension or orthostatic hypotension, tachy- or brady-arrhythmias, acute or chronic pulmonary disease or neuromuscular disorders affecting respiration.
- 3. Cardiac resynchronization therapy (CRT) during index hospitalization, or planned CRT or valve surgeries within the following 6 months.
- 4. Previous or planned implantation of left ventricular assist devices or heart transplant.
- 5. Chronic use of intravenous inotropes.
- 6. Recent (<14 days) use of immunosuppressive or anti-inflammatory drugs (including oral corticosteroids at a dose of prednisone equivalent of 0.5 mg/kg/day but not including inhaled or low dose oral corticosteroids or non-steroidal anti-inflammatory drugs).
- 7. Chronic inflammatory disorder (including but not limited to rheumatoid arthritis, systemic lupus erythematosus).
- 8. Active infection (of any type), including chronic/recurrent infectious disease (i.e. HBV, HCV, and HIV/AIDS) – but excluding HCV+ with undetectable plasma RNA.
- 9. Evidence of COVID19 within the last 60 days or recent (21 days) exposure to close personal contact.
- 10. Current malignancy (excluding carcinoma in situ [any location] or localized non-melanoma skin cancer) receiving targeted therapy
- 11. Any comorbidity limiting survival or ability to complete the study.
- 12. Stage V kidney disease or on renal-replacement therapy.
- 13. Neutropenia (<1,500/mm³ or <1,000/mm³ in African-American patients).
- 14. Pregnancy.
- 15. Angina, hypertension, arrhythmias, electrocardiograph (ECG) changes, or other non-cardiac limitations (i.e., peak respiratory exchange ratio VCO₂/VO₂ [RER]<1.0, reflecting sub-maximal test) that limit maximum exertion during CPX obtained during the baseline testing.
- 16. Hypersensitivity to Kineret or to E. coli derived products.

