7.3 Investigational treatment

Anakinra or placebo (vehicle) dispensed in small syringes (0.67 mL) will be provided to the patient for daily subcutaneous injection. The syringes for anakinra or placebo will be undistinguishable. This will be achieved by assuring that the syringes provided by the supplier (Swedish Orphan Biovitrum, Stockholm, Sweden) are labeled only by a number or other code. If the supplier is unable to provide placebo syringes that are indistinguishable, then the pharmacist will transfer the content of each syringe into an unlabeled syringe which will then be marked in a way that neither the patient nor the physician will be able to distinguish between anakinra or placebo.

After completion of all baseline testing, patients will be given a 14-day supply of anakinra or placebo. Additional syringes from the initial batch may be given to assure that the patient has a sufficient number to last until the 14-day follow up visit, which will be scheduled within 14 ± 3 days after baseline visit. Patients will also receive instruction from the investigators regarding self-injection technique. The next set of syringes (for another 4 ± 1 weeks of treatment) will be given to the patient at the time of 14-day follow-up visit. If needed, the first 2 sets of syringes (6 ± 1 weeks) may be dispensed at the same time. A third set of syringes (for another 6 ± 1 weeks of treatment) will be given at time of the 6 weeks visit. A final set of syringes (for another 12 ± 2 weeks) will be given at the 12-week visit.

Adherence to the investigational treatment will be addressed by count of syringes and completion of all study visits. All concomitant medications will also be recorded at each clinic visit. Patients in the study will receive guidelines-based medical treatments as indicated. Such treatments may include diuretics, β -adrenergic receptor blockers, angiotensin converting enzyme inhibitors, angiotensin receptor blockers, neprilysin inhibitors, aldosterone blockers, isosorbide dinitrate, hydralazine, digoxin, ivabradine, aspirin, and statins. For such medications, we will record the start date and the daily dose, and any change in dose or suspension.

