7.9 Study Schedule

	Screening (≤14 days from discharge)	Visit 1 (Baseline)	Visit 1.5 (14±3 days)	Visit 2 (42±7 days)	Visit 3 (84±7 days)	Visit 4 (128±14 days)
Visit location	Hospital or CRSU	CRSU	CRSU***	CRSU	CRSU	CRSU
Screening *	X					
Consent	X					
Clinical assessment **	X	X	X	X	X	X
Medication reconciliation	X	X		X	X	X
Investigational therapy dispensing		X		X	X	
CPX		X		X	X	X
Echocardiogram		X		X	X	X
Non-invasive hemodynamics/ Bio-Impedance		X		X	X	X
Safety labs (CBC, renal function)		X	X	X	X	X
Biomarkers (hsCRP, NTproBNP)		X		X	X	X

*Includes hsCRP - Pregnancy test will be performed, if indicated

**Clinical assessment includes history and physical, medication reconciliation, and assessment of adverse events

***Visit 1.5 may happen in the CRSU or in other clinics with the patient's own provider.

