9.2 Definition of the events

The events adjudicated will include:

- Death;
- Cardiac death (in which a direct cause attributable to cardiac disease is present);
- Sudden cardiac death (in which cardiac death occurred out of the hospital and suddenly; or in the hospital due to ventricular arrhythmias unrelated to other concomitant cardiac conditions);
- Non-cardiac death (in which the event of death is considered not to be a direct consequence of cardiac disease);
- Hospitalization for any cause;
- Hospitalization for heart failure (in which the primary diagnosis for hospitalization is decompensated heart failure established as the finding at admission of all 2 conditions listed: *a.* dyspnea or respiratory distress or tachypnea at rest or with minimal exertion; *b.* evidence of elevated cardiac filling pressure or pulmonary congestion (at least one of the conditions must be met: pulmonary congestion/edema at physical exam OR chest X-ray; plasma BNP levels ≥ 200 pg/ml; or invasive measurement of left ventricular end-diastolic pressure > 18 mmHg or of pulmonary artery occluding pressure (wedge) > 16 mmHg);
- Outpatient worsening of heart failure (defined as the need for intravenous diuretic treatment or need for increase in oral diuretic dose, or new prescription for first or add-on diuretic);
- Acute myocardial infarction, as defined by the WHO consensus statement 4th edition;
- Unstable angina, or need for coronary revascularization;

- Cardiac tachy-or brady-arrhythmias leading to a new hospitalization or to prolongation of hospital stay;
- Acute renal failure (defined as an increase in plasma creatinine levels of 50% or 0.5 mg/L);
- Acute respiratory failure (not due to heart failure);
- Sepsis or other serious infection requiring antibiotic therapy;
- Acute stroke.

The analysis will consider time to first event and time to each event. It will also consider event rates at 1, 3 and 6 months, in order to favor comparisons with other studies. The number of days free of hospitalization during the first 1, 3 and 6 months will also be measured and compared between groups.

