10.1 Reasons for Discontinuation of Treatment or Withdrawal from the Study

Patients may withdraw from the study at any time. The investigators may temporarily suspend treatment at any time in patients experiencing an adverse event considered possibly, probably, or definitely related to the study drug. The study drug may then be restarted upon resolution of the adverse event unless the adverse event is considered likely to reoccur or the patient is unwilling to restart treatment. The investigators can withdraw any patient at any time from the study if medically necessary. It will be extremely important to obtain complete follow-up data on each patient, except on those who withdraw consent to release such information. It will be documented whether or not each patient completed the study. If for any reason the study treatment or observations were discontinued, the reasons will be recorded and the IRB will be informed.

Reasons for discontinuation of Anakinra (or placebo):

- 1) Systemic infection (sepsis)*;
- 2) Surgery*;
- 3) New diagnosis of cancer that requires local or systemic treatment;
- 4) Hypersensitivity reaction (rash, anaphylaxis, arthritis);
- 5) Severe injection site reactions*;
- 6) Need for immunosuppressant therapy;
- 7) Acute myocardial infarction or stroke*;
- 8) Severe neutropenia (<1,000/mm³) if there is a perception of increased infectious risk by the provider*.

* treatment may be restarted by investigators after the condition is resolved

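### Section 8.3.1 describes every-other-day anakinra in severe renal impairment, but Section 2 and Section 7.3 assign daily injection to everyone, and no text says which applies

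*Combined protocol and SAP*

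**What the plan says.** Four parts of the protocol bear on how often a participant with poor renal function injects.

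- **Drug description (Section 8.3.1).** Anakinra 100 mg is described as given "daily or every other day in patients with severe impairment in renal function". The same paragraph says that age, weight and liver failure call for no adjustment.
- **Assigned regimen (Section 2 and Section 7.3).** The summary gives "allocation to Anakinra 100 mg daily or placebo in 2:1 ratio for 24 weeks". Section 7.3 says that syringes of anakinra or placebo "will be provided to the patient for daily subcutaneous injection". Neither mentions renal function.
- **Eligibility (Section 6.3).** Criterion 12 excludes "Stage V kidney disease or on renal-replacement therapy". Criterion 11 excludes "Any comorbidity limiting survival or ability to complete the study", and criterion 2 covers comorbidities that would interfere with running or interpreting the study. Criteria 2 and 11 depend on judgement and set no renal threshold.
- **Monitoring and stopping.** Renal function is a safety laboratory test at Visits 1, 1.5, 2, 3 and 4 (Section 7.9). Acute renal failure is an adjudicated event (Section 9.2). None of the eight reasons for discontinuing treatment in Section 10.1 is renal.

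**The concern.** Two descriptions of the schedule stand in one protocol, and they differ for a group of patients that the eligibility criteria do not clearly remove. Staff who follow Section 7.3 as written could keep a participant on a schedule at odds with the protocol's own account of how the drug is given. Staff who act on Section 8.3.1 would depart from the assigned regimen. What is at stake is participant safety and uniform exposure within the anakinra arm. There is also a practical matter: dispensing is described only for daily injection, and adherence is followed partly by counting syringes.

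**Working it through.** The plan states no statistical figure on this point, so the check is a comparison of passages, plus one piece of arithmetic for scale.

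**Step 1: do the dosing passages agree?** For a participant without severe renal impairment, Sections 2, 7.3 and 8.3.1 all give daily injection. For a participant with severe impairment, Section 8.3.1 gives every other day, while Sections 2 and 7.3 still give daily. The mismatch is confined to that group.

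**Step 2: can anyone in that group be in the trial?** The protocol gives no stage, filtration rate or creatinine level for severe impairment, so there are two cases.

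| Meaning of severe | At entry | After decline on study |
|---|---|---|
| Includes some impairment short of stage V | Patients can be eligible, unless removed by judgement under criterion 2 or 11 | Both descriptions apply |
| Stage V only | Excluded by criterion 12, so about none | Both descriptions can still apply, because criterion 12 acts only at entry |

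**Step 3: does another passage settle it?**

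- Section 7.9 schedules renal function tests but links no result to injection frequency.
- Section 8.1 lists renal function among the heart-failure data to be assessed and allows treatment changes for side effects without unblinding. It names no renal rule.
- Section 10.1 lets investigators suspend treatment for an adverse event at least possibly related to study drug, and withdraw a patient when medically necessary. Neither provision sets a frequency. Section 8.3.1 also says that expected events of the disease's natural history are not adverse events, so renal decline put down to heart failure might not reach the suspension clause.
- By contrast, Sections 8.1 and 10.1 give neutropenia numerical thresholds and actions. The protocol does write laboratory-driven rules elsewhere.

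No passage resolves the mismatch.

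**Step 4: scale for one affected participant.** 24 weeks × 7 days = 168 days. Daily injection gives 168 injections; every other day gives 168 / 2 = 84. The ratio is 168 / 84 = 2.

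**Step 5: effect on the statistics.** The sample size in Section 11.2 rests on 68 and 34 patients, a difference of 1.6 mL/kg/min, a standard deviation of 1.7 to 2.0 and 20% loss. None of these is an injection frequency. Section 11.3.1 analyses patients in the groups to which they were randomised. Neither changes.

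**The case against.** The strongest reply is that the sentence in Section 8.3.1 is product background. It sits in a paragraph on the drug's known risks, names anakinra alone where the operative treatment rules cover anakinra or placebo, and carries no link to the trial. The regimen is set in Sections 2 and 7.3, which agree with each other. This may well be the intended reading, but the protocol does not say so. The same paragraph does turn background into a trial rule for pregnancy, by adding that pregnant women are excluded, and offers nothing comparable for renal function. The ambiguity stands.

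Other parts of the reply are right and limit the point:

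- A reader might infer that the eligibility criteria contradict the dosing text. They do not. Criterion 12 is consistent with every dosing passage; it matters only because it leaves some patients exposed to the mismatch.
- A reader might infer that adherence would be calculated on a wrong denominator. The protocol defines no expected count, adherence percentage or adherence-based analysis. Section 7.3 says only that syringes are counted and visits completed.
- A reader might want to put a percentage on the patients affected. The documents give no basis for one.
- Acute renal failure in Section 9.2 is a rise in creatinine, not a level of severe impairment, and under Section 9.3 adjudication comes after the study and has no bearing on its conduct. It shows that renal decline was foreseen, and no more.

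**Conclusion.** The point holds as an unresolved inconsistency between Section 8.3.1 on one side and Sections 2 and 7.3 on the other. It concerns participants with renal impairment short of stage V and participants whose renal function declines on treatment. How many there are cannot be derived from the documents: near zero at entry if severe means stage V, more if it means less than that, and unknown for decline on study. For each one the schedules differ about twofold. The conclusion rests on the absence of any definition of severe impairment and of any text that gives one passage priority. It takes no view on which schedule is right. It should be corrected because it bears on safety and uniform exposure, but it does not threaten power or the primary analysis.

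**What to change.** Reconcile Sections 2, 7.3 and 8.3.1 by stating whether the every-other-day wording applies in this trial.

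- **If it applies:** define severe impairment, say what happens when renal function declines on study, apply the rule identically in both blinded arms, and align the dispensing and syringe-count text in Section 7.3.
- **If it does not apply:** say in Section 8.3.1 that the sentence is general product information and that Section 7.3 sets the trial regimen.

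The sponsor and medical lead decide which passage holds. The cost is a wording amendment. Renal function is already tested from baseline to Visit 4, so no new measurement is needed, and the sample size and analysis stay as they are.
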